#### Tests

check for negative urine b-HCG for females of child-bearing potential

Record baseline laboratory tests (within 3 months of treatment week 0) and date of tests: haemoglobin, platelets, bilirubin (total), alanine transaminase (ALT) albumin, creatinine, eGFR (Cockcroft-gault or MDRD formula)

A log of participants who are screened but not randomised should be documented. For CONSORT reporting, those not randomised should have demographic data (age, gender, ethnicity), whether enrolled, documented. The reason for not undergoing randomisation should be documented.

#### 13.5 Patient Allocation

#### 13.5.1 Randomisation Method

Participants who fulfill inclusion/ exclusion criteria will be randomised. This takes place anytime after enrolment between treatment week 8 to 12. Sites must ensure sufficient time to randomise participants and dispense additional IMP for those in the arm B (24 weeks) such that there will not be more than 24 hours before commencing week 13 treatment.

Participants will be allocated into treatment arms A and B in a 1:1 ratio, by block randomisation, and stratified by whether they have compensated cirrhosis or decompensated cirrhosis at baseline. Participants with previous history of decompensation will be considered as having decompensated cirrhosis for the purpose of stratification. This is in order to generate equal numbers within each arm, with balanced severity of liver disease distributed. Clinical trial data suggests that severity of liver disease and presence of decompensated cirrhosis are one of the most important factors determining treatment outcome [8].

There may be other patient factors which influence treatment success, but further stratification for a study of 60 participants would not be appropriate. Block randomisation will enable interim analysis to be performed with balanced groups.

#### 13.5.2 Randomisation Procedure

Stratified block randomisation will be performed using a computer or web-based system. This will be performed by the Pragmatic Clinical Trial Unit, QMUL, with a trial-specific randomisation procedure. Anonymised randomisation outcome can be accessed by the trial coordinator and/or study investigator.

Unblinding or emergency access to randomisation codes will not be required for this open-label study.

13.5.3 Cohort allocation/sequential allocation

NA

13.6 Blinding

NA

13.7 Unblinding

NA

13.8 Trial Schedule

13.8.1 Schedule of Treatment for each visit

13.8.2 Schedule of Assessment (in Diagramatic Format)

Study Visits Schedule for Arm A – 12 weeks of sofosbuvir/velpatasvir							
	Treatment week	0-8	8-12	12	16	20	24
	Visit windows			+/- 7 days	+/- 14 days	+/- 14 days	+ 28 days
Assessments		Pre-	Screening/	End of	Post	Post	End of
		enrolment	baseline	treatment	treatment	treatment	study
NHS treatment visits		х					
Informed consent			х				
Review inclusion/exclusions	Supply participant card		х				
Randomisation			х				
Pregnancy test (if applicable)	Urine test		х				
Document contraception/ breastfeeding advice (if applicable)			х	х	х		
Record demographics			х				
History			х				
Physical examination	Cardiovascular		Х				
	Respiratory		X				
	Gastrointestinal		X				
Review concomitant medications			X	х			
Prescription and dispensing of NHS treatment		х					
Prescription and dispensing study drugs							
Drug accountability	Record missed doses		х	х			
Adverse events recording	Events since week 0		х				
C	Events since last visit			x	x	x	x
Laboratory samples	FBC			Х	Х	Х	Х
	Urea & electrolytes,			Х	Х	X	Х
	creatinine			Х	Х	X	X
	LFTs			Х	Х	X	X
	Albumin			Х	x	x	X
	HCV RNA			Х	(optional)	(optional)	Х
Quality of life questionnaire				x			x

Study Visits Schedule for Arm B – 24 weeks of sofosbuvir/velpatasvir							
	Treatment week	0-8	8-12	12	16	20	24
	Visit windows			+/- 7 days	+/- 7 days	+/- 7 days	+/- 7 days
Assessments		Pre-	Screening/	Study	Study	Study	End of
		enrolment	baseline	treatment	treatment	treatment	treatment
NHS treatment visits		х					
Informed consent			х				
Review inclusion/exclusions	Supply participant card		х				
Randomisation			х				
Pregnancy test (if applicable)	Urine test		х				
Document contraception/			х	х	х	X	Х
breastfeeding advice (if applicable)							
Record demographics			х				
History			х				
Physical examination	Cardiovascular		X				
	Respiratory		X				
	Gastrointestinal		X				
Review concomitant medications			X	х	X	X	X
Prescription and dispensing of NHS		x					
treatment							
Prescription and dispensing study				Х	Х	X	Х
drugs							
Drug accountability	Record missed doses		х	х	Х	X	Х
Adverse events recording	Events since week 0		x				
	Events since last visit			х	х	х	х
Laboratory samples	FBC			X	X	X	X
	Urea & electrolytes,			Х	Х	X	Х
	creatinine			X	Х	X	Х
	LFTs			X	Х	X	Х
	Albumin			x	x	x	Х
	HCV RNA			(optional)	(optional)	(optional)	х
Quality of life questionnaire							X

	Treatment week	28	32	36
	Visit windows	+/- 14 days	+/- 14 days	+ 28 days
Assessments		Post treatment	Post treatment	End of study
NHS treatment visits				
Informed consent				
Review inclusion/exclusions				
Randomisation				
Pregnancy test (if applicable)	Urine test			
Document contraception/ breastfeeding advice (if applicable)		х		
Record demographics				
History				
Physical examination	Cardiovascular Respiratory Gastrointestinal			
Review concomitant medications				
Prescription and dispensing of NHS treatment				
Prescription and dispensing study drugs				
Drug accountability	Record missed doses			
Adverse events recording	Events since week 0			
	Events since last visit	X	X	Х
Laboratory samples	FBC	Х	X	Χ
	Urea & electrolytes,	X	X	Χ
	creatinine	X	X	Χ
	LFTs	X	X	Χ
	Albumin	X	х	Χ
	HCV RNA	(optional)	(optional)	X
Quality of life questionnaire				X

#### 13.8.3 Trial assessments

#### **Pre-Screening**

All adult patients infected with genotype 3 HCV with cirrhosis (see eligibility for definition), who commenced on NHS treatment with sofosbuvir/velpatasvir, with HCV RNA above or equal to 30 iu/mL at treatment week 2 (+/- 3days) can be considered for study entry. Clinicians will inform patient of their slow response to therapy, risk of treatment failure and potential improvement with extended treatment, and offer enrolment in the study. If patient accepts invitation, clinician will contact the study team to provide the Patient Information Sheet for his or her to review.

#### Screening/baseline

Treatment weeks 8 up to 12

After a patient gives informed consent to participate, the following will be performed:

- document date when participant receives PIS (at least 24 hours before consent)
- 3 copies of informed consent signed
- enter participant into screening log (for those not enrolled, document reason e.g. not fulfilling inclusion/exclusion criteria)

Note consent must be taken by a study doctor.

#### Determine inclusion / exclusion criteria

- document genotype, baseline HCV viral load and date(last result prior to treatment week 0, must be >10,000 iu/mL to be eligible), HCV viral load at treatment week 2 (+/-3 days)
- document criteria used to determine cirrhosis or decompensated cirrhosis from clinical records
- document any imaging (e.g. ultrasound / CT / MRI, with dates ) within 6 month before treatment start, if available – to determine presence of hepatocellular carcinoma
- document hepatitis B virus and HIV status
- for females of child-bearing potential only urinary pregnancy test negative
- document contraception and breast-feeding advice in the medical records
- document complete medical, surgical and psychiatric history and study doctor assessment of whether subject is eligible
- document baseline (within 3 months of treatment week 0) laboratory tests eGFR must be
   >30ml/hr and patient not requiring dialysis
- document alcohol and illicit drug use and study doctor assessment of whether subject is eligible

#### Document demographics

- date of birth
- gender
- ethnicity (Caucasian, Asian, Oriental, Afrocarribean, others)

#### Obtain history

- previous HCV treatment experience (pegylated interferon/ribavirin; clinical trial; DAA) note participants exposed to SOF (or other NS5B inhibitor) or DCV (or other NS5A inhibitor) are excluded
- document responses and any adverse events or intolerances to previous treatment, if known

Physical examination - full examination of the cardiovascular, respiratory, gastrointestinal systems as minimum. Assessment of whether the subject has active hepatic decompensation. Other systems as deemed appropriate by investigator.

This should be completed by a study doctor.

Record concomitant medications including over the counter and herbal medications

- review drug-drug interactions (see protocol Trial Medication section, sofosbuvir/velpatasvir SmPC and www.hep-druginteractions.org for guidance)
- prohibited concomitant medications must be discontinued at least 21 days before treatment start as per Exclusions section of protocol
- other investigational medicinal products within 6 weeks of treatment start are excluded
- record if known allergy to any of study drugs

Document if participant is pregnant, breastfeeding, or wishing to conceive during the study treatment period + 30 days after

Document contraceptive and breast feeding advice (if applicable) and currently in use or chosen method of protocol specified contraception.

Record baseline laboratory results and dates (within 3 months of treatment start)

- haemoglobin
- platelet count
- urea & electrolytes, creatinine
- eGFR (using Cockcoft-Gault or MDRD formula) NB eGFR <30ml/hr is an exclusion

- total bilirubin
- ALT
- INR or PT (include lab reference PT range), if available
- Albumin

Record the following regarding current treatment

• start date of sofosbuvir/velpatasvir (treatment week 0)

Record the following between treatment start and screening visit

- Any adverse events/ serious adverse events
- Any treatment discontinuation (of Sofosbuvir/velpatasvir)
- Any missed doses of treatment reported note patient must have at least 90% adherence at screening
- Record batch/lot number and expiry of NHS dispensed bottle of sofosbuvir/velpatasvir

Study doctor must assess whether subject fulfils eligibility.

Note: enrolled participants will complete sofosbuvir/velpatasvir dispensed as part of their NHS treatment and are not dispensed additional study drug, unless they are randomised to the extended treatment arm.

Investigators should review administration instructions with participant and remind them to bring empty bottle for pill check at the next visit.

#### Study assessments

Once enrolled (treatment weeks 8 up to 12), participants will be randomised. Randomisation must occur before the last dose of treatment at week 12 so that participants in the 24 week arm will be supplied with adequate study drugs. Study sites must ensure there is sufficient time to arrange dispensing of additional study drug so that treatment is not interrupted.

After the participant is enrolled they will carry a patient card to identify them as part of the study.

Visits outside of the study schedule are permitted - relevant data will be captured at the next study visit as per protocol.

# Treatment week 12 (study window +/- 7 days) – for arm A (12 weeks) – end of treatment

Record the following between screening visit and end of treatment:

- Concomitant medications review
- Any adverse events/ serious adverse events
- Any treatment discontinuation (of Sofosbuvir/velpatasvir)
- Any missed doses of treatment reported investigators will perform pill count and review returned empty bottles

If participants have left over medication, at the discretion of the study doctor they can complete the remainder tablets, but the end of treatment visit must take place within 7 days of completing medication.

Perform blood samples - FBC, U&Es, creatinine, LFTs, albumin, HCV viral load

Document contraception advice and currently used method (if applicable).

Obtain quality of life questionnaire (SF36) at end of treatment – this does not have to be at the same time as the other visit procedures as long as it is obtained within the visit window

Other procedures or examination performed, as deemed appropriate by investigator, should be recorded in medical notes.

#### Treatment week 12, 16, 20 (study window +/- 7 days) – for arm B (24 weeks)

Record the following between previous visit and this visit:

- Concomitant medications review
- Any adverse events/ serious adverse events
- Any treatment discontinuation (of Sofosbuvir/velpatasvir)
- Any missed doses of treatment reported investigators will perform pill count and review returned empty bottles

Perform blood samples - FBC, U&Es, creatinine, LFTs, albumin. HCV viral load is optional – record if available

Document contraception advice and currently used method (if applicable).

Dispense study medication

- Drugs are prescribed and dispensed every 28 days
- Record batch or lot number, expiry date of dispensed drugs, and date of dispensing
- review administration instructions with participant

Participants who have lost or insufficient medication, at the discretion of their investigator, can have the next due prescription dispensed early. Missing doses should be recorded. (see section 15.19 on assessment of compliance).

Other procedures or examination performed, as deemed appropriate by investigator, should be recorded in medical notes.

Treatment week 24 (study window +/- 7 days) – for arm B (24 weeks) – end of treatment

Record the following between screening visit and end of treatment:

- Concomitant medications review
- Any adverse events/ serious adverse events
- Any treatment discontinuation (of Sofosbuvir/velpatasvir)
- Any missed doses of treatment reported investigators will perform pill count and review returned empty bottles

If participants have left over medication, at the discretion of the study doctor they can complete the remainder tablets, but the end of treatment visit must take place within 7 days of completing medication.

Perform blood samples - FBC, U&Es, creatinine, LFTs, albumin, HCV viral load

Document contraception advice and currently used method (if applicable).

Obtain quality of life questionnaire (SF36) at end of treatment – this does not have to be at the same time as the other visit procedures as long as it is obtained within the visit window

Other procedures or examination performed, as deemed appropriate by investigator, should be recorded in medical notes.

Post-treatment follow up - treatment week 16 & 20 (+/-14 days) for arm A (12 weeks) or treatment week 28 & 32 (+/-14 days) for arm B (24 weeks)

Record the following since the last study visit

• Any serious adverse events

Perform blood samples - FBC, U&Es, creatinine, LFTs, albumin, optional HCV viral load

Document contraception advice and currently used method (if applicable) – required up to 30 days after last dose of study drug.

Other procedures or examination performed, as deemed appropriate by investigator, should be recorded in medical notes.

End of study - treatment week 24 (+ 28 days) for arm A (12 weeks) or treatment week 36 (+ 28 days) for arm B (24 weeks)

Record the following since the last study visit

Any serious adverse events

Perform blood samples - FBC, U&Es, creatinine, LFTs, albumin, HCV viral load

Obtain quality of life questionnaire (SF36) at end of treatment – this does not have to be at the same time as the other visit procedures as long as it is obtained within the visit window

Other procedures or examination performed, as deemed appropriate by investigator, should be recorded in medical notes.

Study team notifies participant's usual clinician that participant has reached trial endpoints, and returns them to the usual care pathway.

# 13.8.4 Follow up Procedures

After the final study visit at 3 month post-treatment, participants will be returned to their routine clinical care pathway. Investigators will inform the patient's usual clinician of the outcome of antiviral treatment - whether the patient has achieved HCV cure or not, which can be determined based on assessments during this study visit.

Participants who withdraw from the study will be returned to their routine care pathway at the point of withdrawal. They may consent to allow the study team to collect treatment virological outcome (at 3 months post-treatment) from their usual clinician. Participants who withdraw from treatment but consent to continue with study follow-up will be returned to their routine care at 3 months post-treatment.

13.8.5 Qualitative assessments - Nested studies

NA

13.8.6 Radiology Assessments

NA

#### 13.9 Withdrawal criteria

Participants have the right to withdraw consent for study participation at any time. Participants will be informed before enrolment that if they wish to withdraw from the study, or if they are withdrawn for any reasons (such as those listed below), study treatments will be discontinued and no further study procedures or visits will be performed. However, participants will be asked at enrolment to consent to having their treatment virological outcome (SVR at 12 weeks after treatment discontinuation) collected, if available. Participants can opt to withdraw this consent, and withdraw

completely from the study; at this point no further data will be collected. Data obtained up to the point of withdrawal will be kept.

When a participant is withdrawn from the study, this is recorded in the medical notes, along with his or her consent (or withdrawal of consent) for collection of treatment virological outcome data.

Participants who withdraw from the study will be notified that they will discontinue treatment with study drugs, and unused study drugs must be returned. They have the option to continue treatment with sofosbuvir/velpatasvir (or other HCV treatment regimes) as routine NHS standard of care at the discretion of their usual clinician. If a participant withdraws during treatment week 8-12, while taking the NHS-supplied sofosbuvir/velpatasvir, the drugs should be returned according to the local NHS pharmacy policy and they may continue to use the drugs on the advice of their usual clinician.

Participants who experience intolerable toxicity or for other clinical reasons according to the investigator can discontinue the study drugs. Dose reduction of sofosbuvir/velpatasvir is not permitted. Participants who discontinue treatment can remain on the study (for follow up) provided they do not withdraw consent.

Any female participant who becomes pregnant during the treatment period will be withdrawn from treatment. Outcome of pregnancy will be followed up (which may occur after the planned study period), including spontaneous or voluntary termination, birth defects, maternal and/or newborn complications, and will be recorded as a significant adverse event. Any female participant who becomes pregnant during treatment and in the first 30 days after treatment end may remain on the study and be followed up as protocol. Any male participant who has conceived with a female partner during treatment or for 30 days after treatment end may remain on the study, but will be consented to follow up the outcome of the conception.

There are no stopping rules for treatment related to treatment response outcome, i.e. participants should continue the entire treatment duration (12 or 24 weeks depending on treatment arm) regardless of their viral response on treatment. Participants who do not achieve negative HCV RNA viral load at the end of treatment do not have the option to further extend their therapy (or switch to the 24 week arm if they are randomised to the 12 week arm), unless if a participant withdraws from the study, and their usual clinician wishes to extend their treatment. Non-response at the end of 12 weeks treatment is rare with direct acting antivirals.

Reasons for withdrawal from study, if known (participants do not have to state reason to justify decision) should be documented.

Participant may not re-enter the study after withdrawal, unless if no treatment doses are missed.

Withdrawn participants will not be replaced, unless if the Trial Steering Committee or Chief Investigator deem the total sample size to be underpowered for the purposes of the study.

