# 13.10 Early withdrawal

The following should be performed if a participant withdrawals before the end of study:

- document timepoint when withdrawal occurs and if allocated study treatment has been completed
- document reason (if known) by participant or investigator
- document if withdrawal is due to safety reasons (e.g. related to any SAE)

- if withdrawal is during study treatment, document if participant consents to continue with study follow up
- unused study drugs must be returned and destroyed
- participants have the option to continue treatment (or with a different treatment) outside of the study, at the discretion of their usual clinician
- document that data and samples collected until the point of withdrawal will be kept and used
- document if participant consents to the collection of their virological outcome (SVR12) if data is collected outside of the study (e.g. by their usual clinician, regardless of whether or not treatment is continued after withdrawal from the study)
- participant are not allowed to re-enter the study unless if no study drug is missed during the withdrawal period

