# 17.4 Notification and reporting Adverse Events or Reactions

If the AE is not defined as SERIOUS, the AE is documented in the participant's medical notes and CRF and the participant is followed up by the research team.

Recording of AEs should start from the first day of randomisation, to the post treatment 12 week visit. Since participants have commenced treatment on standard NHS care at the time of enrolment, events which occurred prior to enrolment are retrospectively documented.

Serious adverse events which occur during IMP use (i.e. treatment week 13 to 24) and until end of trial (post-treatment week 12) need to be reported. SAEs occurring during treatment but prior to IMP use need to be recorded in medical notes and CRF, but not reported.

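### Section 13.9 contradicts itself on whether stopping treatment ends study visits, and participants who leave the study are asked only for SVR12, so a first SAE after leaving cannot be captured

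*Protocol*

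**What the plan says.** Protocol 13.9 opens with what participants are told before enrolment: if they choose to leave, or are "withdrawn for any reasons (such as those listed below), study treatments will be discontinued and no further study procedures or visits will be performed". It adds one exception, that "participants will be asked at enrolment to consent to having their treatment virological outcome (SVR at 12 weeks after treatment discontinuation) collected, if available".

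Later text in 13.9 reads differently. On toxicity, "Participants who experience intolerable toxicity or for other clinical reasons according to the investigator can discontinue the study drugs", and then "Participants who discontinue treatment can remain on the study (for follow up) provided they do not withdraw consent". Participants who become pregnant come off treatment but are allowed to stay for follow-up.

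Section 13.8.4 makes the distinction that the opening of 13.9 lacks. Those who leave the study go back to routine care at once and may agree to their virological outcome being obtained from the usual clinician. By contrast, "Participants who withdraw from treatment but consent to continue with study follow-up will be returned to their routine care at 3 months post-treatment".

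Section 13.10 has a single early-withdrawal checklist. It asks whether the participant agrees to further study follow-up, whether the reason was safety (an SAE is its example), and whether SVR12 may be collected from outside the study.

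On safety data, 17.4 states: "Recording of AEs should start from the first day of randomisation, to the post treatment 12 week visit". The same section has SAEs reported from the start of trial-supplied drug to post-treatment week 12. Section 19.6 defines the SAE endpoint as the proportion of patients with an SAE over treatment plus follow-up.

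**The concern.** There are two linked problems.

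The first is that 13.9 gives two answers to one question: does a participant who stops for toxicity, another clinical reason or pregnancy keep attending? The opening says no and points to the reasons below it. The text on those reasons says yes. The stricter answer is the one participants hear before they enrol, so someone who stops the drug could reasonably believe that visits are over.

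The second is that, once a participant is outside the study, the plan asks for efficacy and not for safety. None of 13.8.4, 13.9 and 13.10 names SAEs, decompensation or death among the items to be requested. This applies even to a participant who is withdrawn by others and has not refused data collection.

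What is at stake is the SAE proportion, a secondary endpoint. Section 9.2 says it is unclear whether the side effects of longer therapy are justified. Section 19.6 wants everyone who takes at least one extension dose in the tolerability analysis. A participant who leaves would therefore stay in the denominator while a later first SAE could not reach the numerator. Sections 13.9 and 13.10 also let such a participant continue the same drug on the NHS, so exposure may go on unobserved.

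**Working it through.** The plan gives no figure on this point to reproduce. The check is a comparison of passages, with simple arithmetic for scale.

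**1. Do visits continue?**

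| Situation | Opening of 13.9 | Other text |
|---|---|---|
| Toxicity or other clinical reason | Visits end | 13.9 (later), 13.8.4, 13.10: follow-up can continue |
| Pregnancy | Visits end | 13.9 (later): may stay for follow-up; 17.11: may be followed for the primary outcome |
| Participant leaves the study | Visits end | 13.8.4: routine care at once |

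The first two rows conflict and the third does not.

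**2. What is collected after leaving the study?** SVR12, if consent is given (13.8.4, 13.9, 13.10). SAEs are not named in any of the three. Sections 17.4 and 19.6 require them to post-treatment week 12.

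**3. Who can be missed?** The endpoint counts patients with at least one SAE, and 13.9 keeps data obtained before withdrawal. Someone who leaves because of an SAE is already counted. A case is missed only if the participant (a) leaves the study rather than just the drug, and (b) has a first SAE afterwards, before post-treatment week 12.

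**4. How many?** The protocol gives no rate for (a) and (b) together. For scale only, expected participants per arm stopping for an adverse event = 30 × rate:
- At 0.2% (9.1, pooled phase 3 data): 30 × 0.002 = 0.06. That rate comes from 12 weeks of treatment in patients without cirrhosis or with compensated cirrhosis.
- At an assumed 1% to 10%, to allow for decompensated patients and a longer course: 30 × 0.01 = 0.3 to 30 × 0.10 = 3.

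These are drug stops, not missed SAEs. On the later text of 13.9 such participants can stay in follow-up. Participants may also leave for reasons unrelated to adverse events, and no rate is given for that. Section 19.2 does not expect withdrawal to be a major problem.

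**5. Which direction?** Only Arm B takes drug in weeks 13 to 24, so drug-related departures in that period fall there. But 11.6 gives participation of up to 28 weeks in Arm B (16 + 12) against 16 in Arm A (4 + 12). The longer observation raises the chance of recording an SAE in Arm B. The two effects oppose each other, and the protocol does not allow the net effect to be worked out.

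**The case against.** The strongest reply is that the distinction between stopping drug and leaving the study is already in the protocol. Section 13.8.4 states it, later text in 13.9 states it for toxicity and pregnancy, and 13.10 prompts staff to record agreement to further follow-up. Ending visits for someone who leaves respects their consent. Toxicity stops are also counted separately, under the treatment-discontinuation endpoint. Most of this stands. It does not remove the conflict with the opening of 13.9, which is the version participants are told. Nor does it supply a route for SAE data from those who leave without refusing further data collection.

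A reader might infer three stronger things, and the documents support none of them:
- *That every participant stopping for toxicity leaves all visits, so SAEs are lost in those most likely to have them.* The later text lets these participants stay, and an SAE that prompts departure is already recorded.
- *That a given number of Arm B cases, and so a given number of percentage points, would be missed.* The protocol contains no figure from which to derive such a count.
- *That the gap makes 24 weeks look safer.* This ignores the longer observation of Arm B.

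**Conclusion.** The concern holds in a limited form. Section 13.9 contradicts itself on whether visits continue after withdrawal for the reasons it lists, and its opening also conflicts with 13.8.4 and 13.10. For participants who leave the study, the planned data request covers SVR12 only, so a first SAE after leaving goes uncaptured within a window that 17.4 and 19.6 say is covered.

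The effect is probably small. That judgement rests on the low cited rate of stopping for adverse events, on the assumed 1% to 10% range for this sicker population, and on participants who stop drug being kept in follow-up as the later text allows. The net direction of any bias between the arms is not established. The change is still worth making because it is cheap and because consent scope and data collection belong in the protocol and the consent form.

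**What to change.** Reconcile 13.9, 13.8.4 and 13.10 around two separate events:
- *Stopping study drug*: visits and safety follow-up continue by default unless the participant declines.
- *Withdrawing from the study*: visits end.

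Reword the opening of 13.9, and what participants are told before enrolment, so that it no longer says withdrawal for the listed reasons ends all procedures.

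Extend the enrolment consent, and the SVR12 request already planned to the usual clinician, to cover SAEs, hepatic decompensation and vital status to post-treatment week 12. Exempt only those who refuse further data collection. Add the matching item to the 13.10 checklist.

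The cost is protocol and consent-form wording and a few extra fields on a record request that is already planned. The downside is that routine records give less detailed safety data than study visits. The change concerns follow-up and data collection only. It takes no position on when treatment should stop.
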